5.2 EXCLUSION CRITERIA

5.2.1 MEDICAL HISTORY AND CONCURRENT DISEASES

- Fibrolamellar carcinoma or mixed hepatocellular cholangiocarcinoma
- Radiation therapy (eg, I-131 or Y-90) within 4 weeks (2 weeks for radiation for bone metastases) or radionuclide treatment within 6 weeks of starting therapy (subject is excluded if there are any clinically relevant ongoing complications from prior radiation therapy)
- Prior cabozantinib treatment
- Known brain metastases or cranial epidural disease unless adequately treated with radiotherapy and/or surgery (including radiosurgery) and stable for at least 3 months before starting therapy. Eligible subjects must be without corticosteroid treatment at the time of starting therapy.
- Concomitant anticoagulation, at therapeutic doses, with anticoagulants such as warfarin or warfarin-related agents, low molecular weight heparin (LMWH), thrombin or coagulation factor X (FXa) inhibitors, or antiplatelet agents (eg, clopidogrel). Low dose aspirin for cardioprotection (per local applicable guidelines), low-dose warfarin (≤ 1 mg/day), and lowdose LMWH are permitted.
- The subject has uncontrolled, significant intercurrent or recent illness including, but not limited to, the following conditions:
 - a. Cardiovascular disorders including:
 - i. Symptomatic congestive heart failure, unstable angina pectoris, or serious cardiac arrhythmias
 - ii. Uncontrolled hypertension defined as sustained BP > 150 mm Hg systolic, or 100 mm Hg diastolic despite optimal antihypertensive treatment
 - iii. Stroke (including TIA), myocardial infarction, or another ischemic event within 6 months before starting therapy

- iv. Thromboembolic event within 3 months before starting therapy. Subjects with thromboses of portal/hepatic vasculature attributed to underlying liver disease and/or liver tumor are eligible
- b. Gastrointestinal (GI) disorders including those associated with a high risk of perforation, or fistula formation:
 - i. Tumors invading the GI tract, active peptic ulcer disease, inflammatory bowel disease (eg, Crohn's disease), diverticulitis, cholecystitis, symptomatic cholangitis or appendicitis, acute pancreatitis or acute obstruction of the pancreatic duct or common bile duct, or gastric outlet obstruction
 - ii. Abdominal fistula, GI perforation, bowel obstruction, intra-abdominal abscess within 6 months before starting therapy
- Note: Complete healing of an intra-abdominal abscess must be confirmed prior to starting therapy
- c. Major surgery within 2 months before starting therapy. Complete healing from major surgery must have occurred 1 month before starting therapy. Complete healing from minor surgery (eg, simple excision, tooth extraction) must have occurred at least 7 days before starting therapy. Subjects with clinically relevant complications from prior surgery are not eligible
- c. Cavitating pulmonary lesion(s) or endobronchial disease
- d. Lesion invading a major blood vessel including, but not limited to:, pulmonary artery, or aorta). Subjects with lesions invading the portal vasculature are eligible.
- e. Clinically significant bleeding risk including the following within 3 months of starting therapy: hematuria, hematemesis, hemoptysis of >0.5 teaspoon (>2.5 mL) of red blood, or other signs indicative of pulmonary hemorrhage, or history of other significant bleeding if not due to reversible external factors
- f. Other clinically significant disorders such as:
 - i. Active infection requiring systemic treatment, known infection with human immunodeficiency virus (HIV), or known acquired immunodeficiency syndrome (AIDS)-related illness. Subjects with active hepatitis virus infection controlled with antiviral therapy are eligible.
 - ii. Serious non-healing wound/ulcer/bone fracture
 - iii. Malabsorption syndrome
 - iv. Uncompensated/symptomatic hypothyroidism
 - v. Requirement for hemodialysis or peritoneal dialysis
 - vi. History of solid organ transplantation

- Subjects with untreated or incompletely treated varices with bleeding or high risk for bleeding. Subjects treated with adequate endoscopic therapy (according to institutional standards) without any episodes of recurrent GI bleeding requiring transfusion or hospitalization for at least 6 months prior to study entry are eligible.
- Moderate or severe ascites. Note that controlled ascites with stable dose of diuretics in the last month is allowed.
- Corrected QT interval calculated by the Fridericia formula (QTcF) > 500 ms within 7 days before starting therapy

Note: If the QTcF is > 500 ms in first ECG, a total of 3 ECGs should be performed. If the average of these 3 consecutive results for QTcF is ≤ 500 ms, the subject meets eligibility in this regard.

- Inability to swallow tablets
- Previously identified allergy or hypersensitivity to components of the study treatment formulations
- Pregnant or lactating females
- Diagnosis of another malignancy within 2 years before starting therapy, except for superficial skin cancers, or localized, low-grade tumors deemed cured and not treated with systemic therapy
- History of allergy to study drug components.
- Prisoners or subjects who are involuntarily incarcerated
- Subjects who are compulsorily detained for treatment of either a psychiatric or physical (eg. infectious disease) illness
- Inability to comply with restrictions and prohibited activities/treatments.

6. STUDY DRUG(S) AND CONCOMITANT MEDICATIONS

6.1 INVESTIGATIONAL PRODUCTS

An investigational product, also known as investigational medicinal product in some regions, is defined as a pharmaceutical form of an active substance or placebo being tested or used as a reference in a clinical study, including products already with a marketing authorization but used or assembled (formulated or packaged) differently than the authorized form, or used for an unauthorized indication, or when used to gain further information about the authorized form. The investigational product should be stored in a secure area according to local regulations. It is the responsibility of the investigator to ensure that investigational product is only dispensed to study subjects. Authorized personnel according to local regulations must dispense the investigational product only from official study sites. In this protocol, investigational products is cabozantinib.

6.1.1 CABOZANTINIB

Cabozantinib will be initiated at full dose (60 mg/day) and the dose will be modified upon development of adverse events according to the manufacturer's recommendations and continued until symptomatic tumor progression, unacceptable adverse events, patient decision or death.

6.1.2 PACKAGING AND LABELING.

Cabozantinib 60, 40 and 20 mg will be packaged in an open-label fashion and labeled for use in the ACTION clinical trial.

6.1.3 HANDLING AND DISPENSING

The investigational products should be stored in a secure area according to local regulations. It is the responsibility of the investigator to ensure that investigational products are only dispensed to study subjects and only from official study sites by authorized personnel according to local regulations. The product storage manager should ensure that the study drugs are stored in accordance with the environmental conditions (temperature, light, and humidity) as determined by the manufacturer. If concerns regarding the quality or appearance of the study drug arise, the study drug should not be dispensed. Investigational products documentation must be maintained that includes all processes required to ensure drug is accurately administered. This includes documentation of drug storage, administration and, as applicable, storage temperatures, reconstitution, and use of required processes.

6.1.4 DOSE MODIFICATIONS

6.1.4.1 CABOZANTINIB DOSE MODIFICATIONS

Cabozantinib dose reduction

Toxicities will be graded using the NCI CTC version 5.0 (see Appendix 4). All dose modifications will follow pre-defined dose levels as indicated below.

The modifications of cabozantinib dosage will follow the following pre-defined dose levels:

Table 1: Cabozantinib dose reduction

| | | |
|------------------------------|----------|--|
| Dose level 0 (standard dose) | 60 mg po | 1 tablet of cabozantinib every day |
| Dose level -1 | 40 mg po | 1 tablet of cabozantinib every day |
| Dose level -2 | 20 mg po | 1 tablet of cabozantinib every day |
| Dose level -3 | 20 mg po | 1 tablet of cabozantinib every 2 or 3 days |

If a patient experiences several toxicities and there are conflicting recommendations, the recommended dose adjustment, which reduces the dose to the lowest level, should be used.

If a dose reduction has been performed, intra-subject dose re-escalation can be considered (up to the maximum of 60 mg daily dose) at the discretion of the treating investigator provided that the toxicities has resolved to at least CTC-Grade baseline levels.

Table 2 Dose Modification Criteria

| Toxicity | Criteria Recommended Guidelines for Management |
|---|--|
| Grade 1 AEs | Continue study treatment if AE is tolerated |
| Grade 2 AEs which are intolerable and cannot be adequately managed | At the discretion of the investigator, study treatment should be dose reduced or interrupted. Note: It is recommended that dose interruptions be as brief as possible. |
| Grade 3 (except clinically non-relevant laboratory abnormalities) | Study treatment should be interrupted unless the toxicity can be easily managed with a dose reduction and optimal medical care. |
| Grade 4 AEs (except clinically non-relevant laboratory abnormalities) | Subjects should have their study treatment interrupted immediately. Discontinue study treatment unless the following criteria are met: Subject is deriving clear clinical benefit as determined by the investigator and agreed by the Sponsor. Toxicity can be managed with a dose reduction following recovery to Grade 1 (or baseline) and optimal medical care |

AE, adverse event.

^a Study treatment dose adjustment is only needed if the toxicity was deemed related to study treatment or had an unclear relationship to study treatment.

^b For dose reduction levels, see Table 1.

6.1.4.2 GENERAL

The side effect profile of cabozantinib includes GI symptoms (such as nausea, vomiting, and diarrhea, mucositis/stomatitis), fatigue/asthenia, anorexia, weight loss, skin disorders including PPE syndrome, elevated liver function tests (including alanine aminotransferase [ALT] and AST), increased pancreatic enzymes with rare cases of overt pancreatitis, hypothyroidism, QTc prolongation, as well as side effects associated with inhibition of VEGF signaling. The latter of these include arterial and venous thrombotic events such as deep vein thrombosis (DVT), pulmonary embolism (PE), transient ischemic attack, and myocardial infarction; hypertension; hemorrhagic events; proteinuria, wound complications, and rare cases of GI perforation, fistulae formation and rectal/perirectal abscess, osteonecrosis, and reversible posterior leukoencephalopathy (RPLS). Please refer to the Investigator's Brochure for additional details. As with all investigational products, unknown AEs may occur. Subjects should be monitored closely throughout their study participation for all AEs. As with other agents in development, additional AEs are unknown. As of 22 October 2013, in studies with cabozantinib,

angioedema has been reported to occur in ~0.1% of subjects treated. The predicted effective plasma half-life of cabozantinib is 55 hours. Thus, when initiating therapy with cabozantinib, it will take most subjects 2-3 weeks to reach steady state after daily dosing. If AEs attributable to cabozantinib occur within the initial 3-week period of dosing, early intervention with dose modifications may be justified for AEs that, if worsened, could potentially be dangerous or debilitating, since without a dose adjustment, systemic exposure of cabozantinib might be expected to increase after the onset of the AE. Management of fatigue, anorexia, diarrhea, nausea, skin disorders, vomiting, rash, hypertension, proteinuria, elevated ALT and AST, myelosuppression, mucositis, hypothyroidism, and cardiac disorders are presented in this section as these have been observed in previous studies with cabozantinib or represent common class effect toxicity. In addition, guidelines to minimize the risk for potential SAEs such as GI and non-GI perforation and fistula formation, hemorrhagic events, and osteonecrosis of the jaw (ONJ) are provided in this section. Please refer to the Investigator's Brochure for additional practice guidelines and management

recommendations for side effects potentially related to cabozantinib treatment; available information on potential risk of congenital, familial, and genetic disorders; and guidelines on management of cabozantinib overdose.

6.1.4.3 GASTROINTESTINAL DISORDERS

The most common GI AEs reported in clinical studies with cabozantinib are diarrhea, oral pain, dyspepsia, stomatitis, and dysphagia.

Diarrhea

Subjects should be instructed to notify their physician immediately at the first signs of poorly formed or loose stool or an increased frequency of bowel movements. Administration of management. Some subjects may require concomitant treatment with more than one antidiarrheal agent. When therapy with antidiarrheal agents does not control the diarrhea to tolerable levels, study treatment should be temporarily interrupted or dose reduced per Table 2.

In addition, general supportive measures should be implemented including continuous oral hydration, correction of fluid and electrolyte abnormalities, small frequent meals, and stopping lactose-containing products, high fat meals and alcohol. For more information please refer to the current Investigator's Brochure.

Nausea and Vomiting

Antiemetic agents are recommended as clinically appropriate at the first sign of nausea and vomiting or as prophylaxis to prevent emesis, along with supportive care according to clinical practice guidelines. The 5-HT3 receptor antagonists are recommended over chronic use of NK-1 receptor antagonists and dexamethasone (NK-1 receptor antagonists can induce or inhibit CYP3A4, and glucocorticoids induce CYP3A4 and thus could lower cabozantinib exposure. Caution is also recommended with the use of nabilone, which is a weak inhibitor of CYP3A4.

Stomatitis and Mucositis

Preventive measures may include a comprehensive dental examination to identify any potential complications before study treatment is initiated. Removal of local factors should be instituted as indicated, such as modification of ill-fitting dentures and appropriate care of gingivitis. During study

treatment good oral hygiene and standard local treatments such as nontraumatic cleansing and oral rinses (eg, with a weak solution of salt and baking soda) should be maintained. The oral cavity should be rinsed and wiped after meals, and dentures should be cleaned and brushed often to remove plaque. Local treatment should be instituted at the earliest onset of symptoms. Obtain bacterial/viral culture if oral infection is suspected and treat infection as clinically indicated. When stomatitis interferes with adequate nutrition and local therapy is not adequately effective, dose reduction or temporary withholding of study treatment should be considered.

6.1.4.4 HEPATOBILIARY DISORDERS

Elevations of ALT, AST, and total bilirubin have been observed during treatment with cabozantinib. A subject who has ALT, AST, and total bilirubin $\leq 3.0 \times$ ULN at baseline and who develops \geq Grade 3 elevated ALT, AST, or total bilirubin should have study treatment interrupted and the dose reduced as outlined in Tables Table 2.

Subjects on this study may enter the study with elevations of AST/ALT up to $5 \times$ ULN at baseline. Elevations of aminotransferases when hepatic tumors are present may not require dose modifications if there are no progressive changes in the aminotransferases (less than a doubling) and if there are no progressive elevations in serum total bilirubin concentration or coagulation factors. Cabozantinib treatment should be interrupted when transaminase increases are accompanied by progressive elevations of total bilirubin, and/or elevations of coagulation tests (eg, International Normalized Ratio [INR]). More frequent monitoring of transaminases should be considered and study treatment should be held until the etiology of the abnormalities is determined and these abnormalities are corrected or stabilize at clinically acceptable levels. If hepatic toxicity resolves during a temporary hold and was deemed related to study treatment, then study treatment may be restarted at a reduced dose. Study treatment should be discontinued if hepatic dysfunction is not reversible despite temporary interruption of study treatment. Elevations $> 3 \times$ ULN of ALT or AST concurrent with $> 2 \times$ ULN total bilirubin without other explanation can indicate drug-induced liver injury and drug should be permanently discontinued. If possible, hepatotoxic concomitant medications should be discontinued in subjects who develop increased values of ALT, AST, or total bilirubin. Evaluation of subjects with elevated transaminases or total bilirubin should be individualized and guided by the presence of specific risk factors such as illnesses which affect liver function (eg, infectious and non-infectious causes of hepatitis, liver cirrhosis, thrombosis of portal or hepatic vein), concomitant hepatotoxic medication, alcohol consumption, and cancer related causes. AEs which are based on hepatic dysfunction should be managed according to locally accepted clinical practice, including monitoring of appropriate laboratory functions.

6.1.4.5 HEMATOLOGICAL DISORDERS

Hematological toxicities (ie, neutropenia and thrombocytopenia) and associated complications have been observed after administration of cabozantinib and may be managed with dose interruptions and/or dose reductions. Use of granulocyte colony-stimulating factor support for neutrophil recovery is allowed per investigator discretion. Complete blood counts with differentials and platelets should be performed during treatment if necessary. Subjects with hematologic toxicities may require additional or more frequent laboratory tests according to institutional guidelines. Febrile neutropenia or evidence of infection associated with neutropenia must be assessed immediately and treated aggressively

according to institutional guidelines. Dose reductions or dose interruptions for anemia are not mandated but can be applied as clinically indicated. Supportive care such as red blood cell transfusions may be given as clinically indicated.

6.1.4.6 FATIGUE, ANOREXIA, AND WEIGHT LOSS

Fatigue has been reported during treatment with cabozantinib. Common causes of fatigue such as anemia, deconditioning, emotional distress (depression and/or anxiety), nutrition, sleep disturbance, and hypothyroidism should be ruled out and/or these causes treated according to standard of care. Individual nonpharmacological and/or pharmacologic interventions directed to the contributing and treatable factors should be given. Pharmacological management with psychostimulants such as methylphenidate should be considered after disease specific morbidities have been excluded. Note: Chronic use of modafinil should be avoided because of its potential to reduce cabozantinib exposure (see Investigator's Brochure).

Dose reduction of study treatment should be considered when general or pharmacological measures have not been successful in reducing symptoms. Dose interruption may be considered for Grade ≥ 3 fatigue despite optimal management, at the investigator's discretion. Anorexia and weight loss should be managed according to local standard of care including nutritional support. Pharmacologic therapy such as megestrol acetate should be considered for appetite enhancement. Should these interventions prove ineffective, dose hold and reductions may be considered for Grade ≥ 3 anorexia or weight loss. If anorexia and/or weight loss do not recur after a dose reduction, dose of study treatment may be re-escalated to the previous dose.

6.1.4.7 SKIN DISORDERS

Palmar-plantar erythrodysesthesia (PPE) syndrome PPE syndrome (also known as hand-foot syndrome), skin rash (including blisters, erythematous rash, macular rash, skin exfoliation, dermatitis acneiform, and papular rash), pruritus, dry skin, and erythema have been reported in cabozantinib-treated subjects. All subjects on study should be advised on prophylactic skin care. This includes the use of hypoallergenic moisturizing creams, ointment for dry skin, and sunscreen with sun protection factor ≥ 30 ; avoidance of exposure of hands and feet to hot water; protection of pressure-sensitive areas of hands and feet; and use of thick cotton gloves and socks to prevent injury and to keep the palms and soles dry. Subjects with skin disorders should be carefully monitored for signs of infection (eg, abscess, cellulitis, or impetigo). Early signs of PPE syndrome include tingling, numbness, and slight redness or mild hyperkeratosis. Early manifestations include painful, symmetrical red and swollen areas on the palms and soles. The lateral sides of the fingers or peri-ungual zones may also be affected. Adequate interventions are required to prevent worsening of skin symptoms such as blisters, desquamations, ulcerations, or necrosis of affected areas. Aggressive management of symptoms is recommended, including early dermatology referral. Treatment guidelines for PPE related to study drug (referred to as "study treatment") are presented in Table 3. In the case of study treatment-related skin changes, the investigator may request that additional assessments be conducted with the subject's consent. These assessments may include digital photographs of the skin changes and/or a biopsy of the affected skin and may be repeated until the skin changes resolve. Wound Healing and Surgery VEGF inhibitors can

cause wound healing complications and wound dehiscence which may occur even long after a wound has been considered healed. Therefore, surgical and traumatic wounds must have completely healed prior to starting study treatment and be monitored for wound dehiscence or wound infection while the subject is being treated with study drug. Study treatment should be stopped at least 28 days prior to scheduled surgery. The decision to resume study treatment after surgery should be based on clinical judgment of adequate wound healing. Study treatment should be interrupted for any wound healing complication. Study treatment should be discontinued in subjects with serious or chronic wound healing complications.

Table 3 Dose Modification Criteria and Recommended Guidelines for Treatment emergent

PPE Syndrome

| CTCAE v.5.0 Grade | Action To Be Taken |
|--------------------------|--|
| Grade 1 | Study treatment ^a may be continued at the current dose if PPE syndrome is clinically insignificant and tolerable. Otherwise, study treatment should be reduced to the next lower dose level. Start urea 20% cream twice daily AND clobetasol 0.05% cream once daily. Reassess at least weekly; if PPE syndrome worsens at any time or does not improve after 2 weeks, proceed to the intervention guidelines for Grade 2. |
| Grade 2 | Study treatment may be continued if PPE is tolerated. Study treatment should be dose reduced or interrupted if PPE is intolerable. Continue urea 20% cream twice daily and clobetasol 0.05% cream once daily and add analgesics (eg, gamma-aminobutyric acid agonists) for pain control if needed. Reassess at least weekly; if PPE does not improve within 2 weeks or worsens or affects self-care, proceed to the intervention guidelines for Grade 3. |
| Grade 3 | Interrupt study treatment ^a until severity decreases to Grade 1 or 0. Continue treatment of skin reaction with clobetasol 0.05% cream twice daily AND analgesics. Resume study drug at a reduced dose if PPE syndrome recovers to |

Grade \leq 1. Discontinue subject from study if intolerable PPE syndrome recurs at a reduced dose or if PPE syndrome does not improve within 6 weeks.

CTCAE, Common Terminology Criteria for Adverse Events; GABA, gamma-amino butyric acid; PPE, Palmar Plantar Erythrodysesthesia.

^a Study treatment includes both cabozantinib and matched placebo.

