4.1.6 WITHDRAWAL OF CONSENT

Subjects who request to discontinue study treatment will remain in the study and must continue to be followed for protocol specified follow-up procedures. The only exception to this is when a subject

specifically withdraws consent for any further contact with him/her or persons previously authorized by subject to provide this information. Subjects should notify the Investigator of the decision to withdraw consent from future follow-up in writing, whenever possible. The Investigator should explain the withdrawal of consent in detail in the medical records, as to whether the withdrawal is from further treatment with study drug only or also from study procedures and/or post treatment study follow-up, and entered on the appropriate CRF page.

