- Refusal of sexually active fertile subjects (excluding subjects who have been sterilized) to use medically accepted methods of contraception
- Pregnancy of a female subject
- Request by the Principal Investigator
- Subject request to discontinue study treatment
- Significant noncompliance with the protocol schedule in the opinion of the investigator or the Principal Investigator
- The Principal Investigator should be notified of all discontinuations of study treatment as soon as possible. If a subject fails to return for the protocol-defined visits, an effort must be made to determine the reason. If the subject cannot be reached by telephone, at a minimum, a registered letter should be sent to the subject (or the subject's legal guardian) requesting contact with the study site.
- For subjects who withdraw or are withdrawn from study treatment, every effort must be made to continue protocol-specified evaluations and procedures through the post-treatment follow-up and extended follow-up visits unless consent to participate in the study is also withdrawn. All subjects will be followed until death, unless consent to do so is specifically withdrawn by the subject or until a decision by the Principal Investigator is made to stop collection of these data.

If the Investigator consider the option of continue with one of the investigations drugs, the decision to continue with one of the drug-study treatments beyond the criteria mentioned in this point of the protocol should be discussed with the Principal Investigator, Medical Monitor and documented in the study records.

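### The last PPE step in Protocol Table 3 removes the patient from the study, contrary to the protocol's own follow-up rules and to the SAP's treatment-policy estimand

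*Protocol*

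**What the plan says.** Protocol section 6.1.4.7 refers drug-related PPE to Table 3, a ladder by CTCAE grade:

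- **Grade 1.** Dosing may go on unchanged when the PPE is insignificant and tolerable, but "if PPE syndrome worsens at any time or does not improve after 2 weeks, proceed to the intervention guidelines for Grade 2".
- **Grade 2.** The row opens with "Study treatment may be continued if PPE is tolerated"; if it is not tolerated, the dose is reduced or held. Then: "if PPE does not improve within 2 weeks or worsens or affects self-care, proceed to the intervention guidelines for Grade 3".
- **Grade 3.** Hold the drug "until severity decreases to Grade 1 or 0" and restart at a lower dose after recovery to Grade 1 or better. The row ends: "Discontinue subject from study if intolerable PPE syndrome recurs at a reduced dose or if PPE syndrome does not improve within 6 weeks".

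Table 2 (section 6.1.4.1), which covers adverse events in general, says of Grade 1: "Continue study treatment if AE is tolerated". Its Grade 2 row covers only events that are intolerable and cannot be managed.

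The rules for patients who stop cabozantinib are elsewhere. Section 4.1.4 sends everyone who discontinues into follow-up, and section 4.1.5 continues survival follow-up to death or study end. Section 6.1.6 says "All subjects will be followed until death, unless consent to do so is specifically withdrawn by the subject", and then adds that the Principal Investigator may end data collection. Section 4.1.6, on patients who ask to stop, says "Subjects who request to discontinue study treatment will remain in the study and must continue to be followed for protocol specified follow-up procedures". Section 7.2.1 records adverse events until 30 ± 7 days after permanent discontinuation.

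SAP section 8.5 applies a treatment-policy strategy to all primary and secondary endpoints. SAP section 8.5.1 does not censor at treatment discontinuation for that estimand.

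**The concern.** Stopping a drug and leaving a study are different events. The follow-up sections and the SAP rely on that difference, and Table 3 erases it for one toxicity. Patients who reach its last step are selected by how badly they tolerate the drug, so any loss of their data would be informative. In a single-arm trial of 40 patients whose purpose is safety, each such patient counts towards the adverse-event rates and the survival curves. The step is also in an operative table that site staff will consult when PPE occurs.

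**Working it through.** The plan gives no figure on this point, so the check mainly compares texts, with a little arithmetic.

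**1. Is PPE an exception to follow-up?**

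| Protocol section | Kept in follow-up | Exceptions or end points named |
|---|---|---|
| 4.1.4 | all who discontinue | consent withdrawn for all procedures; ability to consent freely lost |
| 4.1.5 | all who stop study drug (survival) | death; end of study |
| 6.1.6 | all who leave, or are taken off, treatment | consent withdrawn; Principal Investigator ends collection |

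No row names PPE or any other toxicity. A patient who meets the last step of Table 3 therefore falls under two instructions that cannot both be followed. Section 4.1.6 supports the same principle but concerns patients who ask to stop, so the conflict rests on the three sections above.

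**2. Do the neighbouring rules use the same words?** The rules for wound complications (also in 6.1.4.7), hypertensive emergency (6.1.4.8), arterial thrombosis (6.1.4.9), QTc prolongation (6.1.4.11), severe bleeding (6.1.4.12) and perforation or fistula (6.1.4.13) all stop study treatment. Table 3 names the study instead.

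**3. Which data would be lost?**

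- *Adverse events.* After a recurrence on a reduced dose, the last dose is recent, so the whole 30 ± 7 day window would be lost. Under the six-week limb, if the clock runs from the start of the hold, 6 × 7 = 42 days have passed. That exceeds 30 + 7 = 37 days, so the loss depends on whether the window starts at the last dose or at the decision to stop for good. In both cases section 7.2.1 asks that ongoing events be followed to resolution or stabilisation, and that includes the PPE itself.
- *Progression and survival.* The three-monthly survival contacts would end, and so would any later imaging. That affects overall survival, post-progression survival and time to progression.
- *Analysis.* A treatment-policy analysis uses what was observed and cannot recover what was never collected. SAP 8.5.1 has rules for loss to follow-up and withdrawn consent, but none for removal ordered by the protocol. SAP 8.6.5.1 analyses the primary rates on available data, so an event never recorded is not counted.

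**4. How many patients?** Number removed = 40 × P(reaching the Grade 3 guidelines) × P(intolerable recurrence at a reduced dose, or no improvement in six weeks, given that). The documents give no value for the last factor, so no estimate can be made.

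**5. The ladder's step-ups (secondary).** Grade 2 PPE unimproved at 2 weeks goes to the Grade 3 guidelines whether or not it is tolerated, although the same row lets tolerated PPE continue. Grade 1 PPE that never improves gets there after 2 + 2 = 4 weeks. Grade 1 already meets the condition that ends the hold, so the instruction is circular. The start of the six-week clock is not stated either. For PPE starting at Grade 2, it expires at week 6 if counted from onset, or at 2 + 6 = 8 weeks if counted from entry to the Grade 3 guidelines.

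**The case against.** The best defence is that the last step is loose wording for stopping study treatment. The follow-up sections are explicit, section 4.1.4 allows only its stated exceptions, and Table 3 is headed as recommended guidelines. The SAP also lists study discontinuation among the intercurrent events handled by treatment policy. Much of this stands. Study treatment is the most plausible meaning, and lost follow-up is the result of a literal reading, not a certainty. But no sentence says which text prevails, and the neighbouring rules show that the authors had the other phrase available. The SAP's strategy also does not help if collection stops.

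A reader might infer four stronger points, which the documents do not support:

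- *That Table 3 contradicts Table 2.* Table 2 has no row for tolerated Grade 2 events, so there is nothing there to contradict. A PPE-specific table that adds time triggers to a general one is ordinary layering. What is missing is a statement of precedence; the tie-break under Table 1 covers only several toxicities with conflicting advice.
- *That stable Grade 1 PPE is forced into interruption.* The circularity shown above means that no hold of any length follows.
- *That stopping on recurrence at a reduced dose conflicts with Table 1.* Table 1 lists dose levels; it does not promise that each will be tried. The QTc rule has a similar stop after recurrence at a reduced dose.
- *That holds and reductions for PPE bias the critical-event rate downwards.* Dose modification is part of the regimen under test, and under treatment policy its effect belongs to the result.

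**Conclusion.** The conflict is real and confined to one operative sentence. Table 3 ends study participation, whereas sections 4.1.4, 4.1.5 and 6.1.6, the adverse-event window in 7.2.1 and the SAP's primary estimand all require data after treatment stops. If sites follow the table literally, the loss is related to toxicity and covers adverse events, progression and survival. If they read it as study treatment, nothing is lost.

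The size cannot be given. A reader might take the phase 3 PPE rates in Protocol section 1.2.2 (46% any grade, 17% Grade 3) and compute 0.17 × 40 = 6.8 patients at risk of removal and (0.46 − 0.17) × 40 = 11.6 at risk of interruption. Those figures only describe how many might have PPE of each severity, if the rates carried over to this different population. The documents give no split between Grades 1 and 2, no share failing to improve and no recurrence rate, so the figures do not measure this problem.

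The ladder's unclear step-ups are a lesser wording point. Nothing here is a judgement on when PPE should lead to a hold, a reduction or a stop.

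**What to change.** Reconcile the last step of Table 3 with sections 4.1.4, 4.1.5 and 6.1.6, so that it concerns study treatment and not study participation. Add a cross-reference there to those sections and to the adverse-event window in 7.2.1. If removal from the study is really intended, the follow-up sections must name it as an exception and SAP 8.5.1 needs a censoring rule for it.

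In the same amendment, the sponsor should state:

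- whether the Grade 2 two-week trigger applies to tolerated PPE;
- what the step-up means for PPE that stays at Grade 1;
- when the six-week clock starts;
- whether Table 3 takes precedence over Table 2 for PPE.

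The clinical content of these answers is the sponsor's choice. The cost is table wording in a protocol amendment and a note to sites. No visits, procedures or patients are added.
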